### **7.3 Subject Population(s) for Analysis**

All eligible subjects shall be included in the analysis.

## **8 Safety and Adverse Events**

### **8.1 Definitions**

The study shall be monitored for Unanticipated Problems and for Adverse Events by the investigator and sponsor.

An Unanticipated Problem shall be defined as:

- Any issue arising during the study involving potential risk(s) to the subjects, which are not considered adverse events.
- Unanticipated Problems shall be reported to the IRB and sponsor within 7 calendar days, unless as described below:
  - Interim analysis, safety monitoring report, publication in literature or other information that indicates an increase in the frequency or magnitude of a given harm, uncovers a new risk, or provides more information about the benefits of the human research.
  - Change in FDA labeling or withdrawal of the device from the market
  - Protocol deviation that harmed participants or indicates participants might be at increased risk of harm. If the protocol deviation was made in order to eliminate an apparent immediate hazard to a participant, the investigator must submit the information to the IRB and sponsor within 24 hours.
  - Complaint of a participant that indicates participants or others might be at increased risk of harm or at risk of a new harm.
  - Finding of Non-Compliance or allegation of Non-Compliance.
  - Protocol deviations: Failure to follow the protocol due to the action or the inaction of the investigator or staff. Exception – If the protocol deviation was taken in order to eliminate an apparent immediate hazard to the participant, the investigator must report the information to the IRB and sponsor within 24 hours.
  - Breach of confidentiality – Must be reported to IRB and sponsor within 24 hours
  - Change to protocol taken without prior IRB review to eliminate an apparent immediate hazard to a participant, must be reported within 24 hours
  - Incarceration of a participant in a protocol not approved to enroll prisoners
  - Complaint of a participant that cannot be resolved by the research team

An Adverse Event shall be defined per 21 CFR Part 803. Any potential adverse event shall be reported to the IRB and sponsor within 7 calendar days, unless the Adverse Event could be considered reportable as a 5-day report, in which case the notification must be made within 24 hours.

- An event that reasonably suggests that a device has or may have caused or contributed to a death or serious injury
- An event that reasonably suggests that a device has malfunctioned and that the device or similar device would be likely to cause or contribute to a death or serious injury if the malfunction were to recur

- A serious injury/serious illness is one that (1) is life threatening, (2) results in permanent impairment of a body function or permanent damage to body structure, or (3) necessitates medical or surgical intervention to preclude permanent impairment of a body function or permanent damage to a body structure.

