### **4.4 Early Withdrawal of Subjects**

Subjects may choose to withdraw from the study at any time, for any reason without penalty or loss of benefit.

Due to the short duration of the subject participation in the study, there is only one (1) foreseeable scenario in which a subject could withdraw prior to completion of the study:

- A subject might withdraw from the subject if use of the device(s) is uncomfortable. Some patients could be claustrophobic and find the treatment uncomfortable.

For any subject that withdraws prior to completion of the study for this reason, the data will be omitted from the final analysis. The subject may be replaced with another subject to ensure that the full sample size is obtained.

Abrupt termination of study treatment is not expected to affect subject safety, therefore no transition procedures are required.

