## **8.2 Recording and Reporting of Adverse Events**

All observed or volunteered adverse events, unanticipated problems involving risks to subjects, and serious or continuing noncompliance with the federal regulations or the requirements or determinations of the IRB will be reported. Investigators will pursue and obtain information adequate to determine the outcome of each adverse event and to assess whether it meets the criteria for classification as a serious adverse event requiring immediate notification to the sponsor, Investigational Review Board and FDA. Sufficient information will be obtained by the investigator to determine and assess the causality of adverse event. This study will be reviewed at set checkpoints, as specified in the research plan, by the principal investigators.

The sponsor has a duty to report adverse events to FDA per 21 CFR Part 803 and maintains SOP's detailing these requirements. Any adverse event reported to FDA by the sponsor related to a study subject will also be transmitted to the IRB.

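### The adverse event definition in 8.1 is limited to device-reporting criteria, so the discomfort and claustrophobia foreseen in 4.4 may go uncounted as adverse events

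*Combined protocol and SAP*

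**What the plan says.** Section 8.1 sets the definition in one sentence: "An Adverse Event shall be defined per 21 CFR Part 803". The criteria that follow are of two kinds. The first is "An event that reasonably suggests that a device has or may have caused or contributed to a death or serious injury". The second is a malfunction that "would be likely to cause or contribute to a death or serious injury if the malfunction were to recur". A serious injury is then described as one that threatens life, leaves permanent impairment or damage, or needs medical or surgical intervention to prevent that.

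Section 8.1 also has a separate class, Unanticipated Problems, for issues that carry potential risk to subjects and are not adverse events. These go to the IRB and sponsor within 7 calendar days.

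Section 8.2 calls for every adverse event that is observed or volunteered to be reported, and has investigators "assess whether it meets the criteria for classification as a serious adverse event requiring immediate notification".

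Section 4.4 names one foreseeable reason for leaving early: "A subject might withdraw from the subject if use of the device(s) is uncomfortable". It adds "Some patients could be claustrophobic and find the treatment uncomfortable". For subjects who leave for this reason, "the data will be omitted from the final analysis", and they may be replaced.

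**The concern.** The reactions that the protocol itself expects are non-serious, and the definition of an adverse event is written around serious harm. If site staff apply 8.1 literally, a subject who stops because a vest is uncomfortable or brings on claustrophobia has had no adverse event.

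The trial compares the sponsor's device with a competitor's, both at maximum settings. Section 1.4 already cites zero reported adverse events for the AffloVest since 2014. A zero from this study could be read as evidence that both devices are well tolerated, when it may only reflect a definition that does not ask about tolerability. Any difference between the devices in mild reactions could be lost in the same way. The definition also helps determine what triggers the review in 8.5, which follows an Unanticipated Problem or an Adverse Event.

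**Working it through.** The plan gives no figure to reproduce. The 10 subjects in the Study Summary have no calculation behind them (7.1), and there is no safety endpoint (3.2), safety analysis (7.2) or assumed event rate. The check is therefore mainly a comparison of texts, followed by an illustration.

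**Step 1: the foreseen events against the 8.1 criteria.**
- *Death or serious injury.* Ordinary discomfort or claustrophobia that ends when the vest comes off is not life threatening, leaves no permanent impairment or damage, and needs no intervention to prevent either. Not met.
- *Malfunction.* A vest that is uncomfortable while working as intended has not malfunctioned. Not met.

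**Step 2: 8.1 against 8.2.** Section 8.2 sorts adverse events by seriousness. Under 8.1, the first criterion already concerns death or serious injury. The only event without a serious outcome is a malfunction that harmed nobody. No non-serious symptom reaches the sorting step, although 8.2 reads as if such events would be present.

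**Step 3: other places where a mild event might be recorded.**

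| Section | What it offers | Why it is not a reliable count |
|---|---|---|
| 8.1, Unanticipated Problems | Residual class, including some participant complaints | Requires potential risk; is a reporting route; gives no count by device; discomfort already expected in 4.4 does not clearly belong |
| 8.1, 7-day rule | Covers potential adverse events | Still uses the 8.1 term |
| 3.2, survey | Six opinion topics: daily use, lifestyle fit, obtrusiveness, mobility, noise, compliance | No listed topic concerns symptoms |
| 6, procedures | Enrolment, spirometry, survey | No step asks about symptoms |
| 9.2, source documents | Spirometry data and survey | No adverse event or withdrawal record is listed |

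**Step 4: illustration of size.** The number of withdrawals and the event rates below are assumptions.

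*Replaced withdrawals.* Take 10 completers (Study Summary), and suppose 2 further subjects stop for discomfort and are both replaced, as 4.4 permits.
- Subjects who wore a device: 10 + 2 = 12.
- Full recording: 2/12 = 16.7%.
- Under the 8.1 criteria, among those analysed: 0/10.
- By device, if both stop during their first device: 2/12 against 0/10 if it was the same device, or 1/11 on each if it was different devices.

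*Chance that full recording of 10 subjects shows at least one mild event*, 1 − (1 − p)^10:

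| Assumed true rate p | Chance of at least one |
|---|---|
| 1% | 9.6% |
| 5% | 40.1% |
| 10% | 65.1% |
| 20% | 89.3% |
| 30% | 97.2% |

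Under a literal reading of 8.1, the adverse event count for such symptoms is zero in every row.

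*What a true zero would mean.* Exact 95% upper limits for 0/10 are 1 − 0.05^(1/10) = 25.9% (one-sided) and 1 − 0.025^(1/10) = 30.8% (two-sided). These hold under any definition and are not evidence that 8.1 is wrong. They show only how little a zero in 10 subjects excludes.

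**The case against.** The strongest reply is that the protocol has more than one net. Potential adverse events are reportable within 7 days. Section 8.2 covers whatever is observed or volunteered, with follow-up of outcome and causality. The Unanticipated Problem class exists for what the adverse event definition leaves out, and 8.5 requires a review after any such problem. A claustrophobic reaction that ends participation could well be reported there. The setting is also modest: one visit of about two hours, healthy adults, and two cleared devices.

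Much of this stands, and it rules out three stronger readings that a reader might infer.
- *That mild events would never be recorded.* The documents do not support this. An investigator who reads 8.2 broadly, or who sees potential risk, may report them.
- *That 8.1 and 8.2 flatly contradict each other because 8.1 admits no non-serious event.* The malfunction criterion requires no injury, so 8.2 has something to sort. The fit is poor, but there is no strict contradiction.
- *That 4.4 removes withdrawals from the safety record.* It omits their data from the final analysis, and the only analysis method described (7.2) is for spirometry. Nothing in 4.4 cancels reporting under 8.2.

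What the reply does not show is a route that reliably captures simple discomfort as an adverse event and attributes it to a device. Each route needs potential risk to be judged present, or relies on a term that 8.1 has already narrowed.

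**Conclusion.** The point holds in a limited form. The 8.1 criteria leave out the non-serious reactions that 4.4 foresees and sit awkwardly with 8.2. Mild events may therefore go uncounted as adverse events, and the study could report zero for both devices after subjects had stopped because of discomfort. The plan should be corrected on this point. The primary spirometry comparison does not use the definition.

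The size cannot be estimated from the documents. The contrast of 0 of 10 with 2 of 12 is an illustration that rests on two assumed, replaced withdrawals, and the plan specifies no such safety table.

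The conclusion assumes that the criteria listed after the definition spell out what 8.1 means by an adverse event. If they were meant only to mark the faster reporting route, 8.1 would still contain nothing beyond the reference to Part 803 to tell site staff that a non-serious symptom counts.

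**What to change.** - **8.1:** define an adverse event as any untoward medical occurrence during the visit, serious or not and device-related or not. Keep the Part 803 criteria only as the threshold for expedited reporting.
- **8.2 and 9.2:** add a record of each event, with the device worn at onset, and name that record as a source document.
- **Reporting:** list all events and all withdrawals for discomfort by device, for everyone who wore a device, including subjects who are later replaced. Give the number who wore each device as the denominator.

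The 7-day reporting rule and the 8.5 review both refer to adverse events, so a wider definition would widen them too. The sponsor and investigator need to reconcile those passages with the new wording; no stopping rule is proposed here.

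The cost is a few sentences, one line on the case report form, a few minor events to record over a two-hour visit, and possibly a less favourable event count.

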## **8.2 Recording and Reporting of Adverse Events**

All observed or volunteered adverse events, unanticipated problems involving risks to subjects, and serious or continuing noncompliance with the federal regulations or the requirements or determinations of the IRB will be reported. Investigators will pursue and obtain information adequate to determine the outcome of each adverse event and to assess whether it meets the criteria for classification as a serious adverse event requiring immediate notification to the sponsor, Investigational Review Board and FDA. Sufficient information will be obtained by the investigator to determine and assess the causality of adverse event. This study will be reviewed at set checkpoints, as specified in the research plan, by the principal investigators.

The sponsor has a duty to report adverse events to FDA per 21 CFR Part 803 and maintains SOP's detailing these requirements. Any adverse event reported to FDA by the sponsor related to a study subject will also be transmitted to the IRB.

## **8.4 Randomization Codes and Unblinding Procedures**

There are no randomization and/or blinding procedures in this trial.

## **8.5 Stopping Rules**

After any Unanticipated Problem and/or Adverse Event, a review shall be performed to determine whether the study should be terminated for individual subject(s), parts or all of the trial. This shall be determined by the investigator.

## **8.6 Medical Monitoring**

No additional medical monitoring shall be performed throughout the duration of study.

## **8.7 Study-Related Injuries**

Adverse events which are reported during execution of this study shall be handled and reported to relevant authorities in accordance with IBC's internal standard operating procedures.

IBC maintains suitable product liability insurance coverage in the event of any claims resulting from a study-related injury.

## **9 Data Handling and Record Keeping**

### **9.1 Confidentiality**

All data collected will remain confidential. Data will be stored securely under the subject's study identification number. All clinical data, images and surgical/procedural data will be de-identified prior to any in-house or public presentation of data or images. Coded data will only be released to those listed as study investigators or support staff. Paper data records will be stored in locked file cabinets in a locked office. All electronic research data will be stored on a researcher database that is password protected and encrypted. The principal investigator, sub-investigators, IRB, the Food and Drug Administration and any applicable regulatory agencies will have access to the study records upon request. If the results of this study are published, the data will be reported collectively without mention of any subject's identity, thereby ensuring subject anonymity.

Standard confidentiality safeguards will be applied, including keeping paper records in locked files, use of electronic security processes (passwords, etc.) for access to electronic data, and limiting access of records to only personnel directly involved in the study

### **9.2 Source Documents**

The following documents shall be considered source documents:

- Subject spirometry measurement data
- Subject survey

### **9.4 Records Retention**

The data and associated identifiers will be kept for up to 5 years in a locked facility accessible only to designated personnel, at which time the data will be destroyed per investigator policy.

## **10 Study Monitoring, Auditing, and Inspecting**

The study will be monitored on an ongoing basis by the investigator. Due to the short nature of the study, no periodic study monitoring, auditing and/or inspecting is planned.

## **11 Ethical Considerations**

The Principal Investigator will manage and administer the study and ensure that the established procedures and protocol for protection of human subjects and IRB requirements are followed in compliance with the Federalwide Assurance for the Protection of Human Subjects, NIH, FDA and OHRP requirements. The principal investigator is an experienced researcher and maintains well-established controls and policies for safeguarding subjects. International Biophysics Corporation also abides by written policies of clinical study ethics and patient protection.
